6.7.2. Secondary Efficacy Analysis

The percentage of subjects with clinical cure at the Test of Cure visit will be presented by treatment group.

The same analysis will be done for the following endpoints:

- Percentage of subjects with a negative fungal culture at the Test of Cure Visit
- Percentage of subjects with a negative fungal culture at the Test of Cure visit as well as individual sign or symptom score of 0 or 1 on each of the scales for pruritus and debris and a score of 0 on each of the scales for fungal elements and pain.
- Percentage of subjects with individual signs or symptoms with a score of 0 or 1 on each of the scales for pruritus and debris and a score of 0 on each of the scales for fungal elements and pain.
- Frequency counts and percentages will be presented for the subject global assessments at Screening/Baseline and Test of Cure by treatment group. A categorical shift analysis (with categories of None, Minor, and Moderate) in the subject global assessment scale scores from the Screening/Baseline to the Test of Cure Visit will also be presented similarly. Only subjects with results at both the Screening/Baseline and the Test of Cure Visit will be considered in the shift analysis.

In addition the subject global assessment will be presented in frequency counts and percentages for all study visits.

If feasible, analyses may also be conducted by fungal organism isolated at Screening/Baseline.

The secondary efficacy analysis will be presented on both the MITT and PP populations.

6.7.3. Other Efficacy Analysis

The counts and percentages of subjects with “subject therapeutic cure” at the Test of Cure Visit will be presented by treatment group. Subjects are defined as reaching “subject therapeutic cure” if they have a negative mycological culture plus “subject clinical cure” for the study ear, where “subject clinical cure” is defined as the absence of all otomycosis signs and symptoms based on subject assessed pruritus.

6.8. Safety Evaluation

6.8.1. Extent of Exposure

The extent of exposure to study drug in each treatment group will be summarized by total number of days of exposure, total number of applications, number of missed applications and number and percentage of subjects who are compliant. A subject will be considered compliant with the dosing regimen if the subject applied 80% to 120% of the expected number of applications while enrolled in the study.

Days of exposure = Date of last study application – Date of first study application + 1

Total Number of Applications:

$2 * (\text{Date of Last Application} - \text{Date of First Application} + 1) - (\text{Number of doses missed as collected on the case report form (CRF)}) + (\text{Number of extra doses as collected on the CRF})$

Total Number of Expected Applications:

$2 * (\text{End of Treatment Visit Date} - \text{Date of Randomization})$.

If the total number of expected applications exceeds 14 for the 7-Day treatment group then the total number of expected applications will be set to 14. If the total number of expected applications exceeds 28 for the 14-Day treatment group then the total number of expected applications will be set to 28.

Compliance will be calculated as a percentage as 100 times the total number of applications divided by the total number of expected applications.

6.8.2. Medical History

Medical history results will only be shown in a by-subject listing.

6.8.3. Adverse Events

All AEs that occur during the study will be recorded and classified on the basis of MedDRA terminology. Treatment-emergent AEs (TEAEs) are defined as AEs with an onset on or after the date of the first study drug application.

TEAEs will be summarized by treatment group, the number of subjects reporting a TEAE, system organ class, preferred name, severity, relationship to study drug (causality), and seriousness. When summarizing AEs by severity and relationship, each subject will be counted once within a system organ class or a preferred term by using the event with the highest severity and greatest relationship within each classification.

Serious AEs (SAEs) will be summarized by treatment group, severity and relationship to study drug, and individual SAEs will be listed by subject. In addition, a list of subjects who prematurely discontinue from the study due to an AE will be provided.

No statistical inference between treatments will be performed on adverse events.

Listings will be presented for all adverse events as well as for serious adverse events, and adverse events leading to discontinuation from the study.

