| Procedures performed at the Test of Cure Visit will include an assessment of clinical signs and symptoms of otomycosis, a subject global assessment, and a fungal culture of the affected ear(s). AEs and concomitant medications will also be assessed. A urine pregnancy test will be performed in women of childbearing potential.  |
| Study Visits:
Screening/Baseline (1 visit); On Treatment (up to 1 visit); End of Treatment (1 visit); Test of Cure (1 visit)   |
| Efficacy Evaluations: 

• Clinical signs and symptoms of otomycosis (pruritus; debris; presence of fungal elements; pain)

• Fungal culture

• Subject global assessment

  |
| Safety Evaluations: 

• AEs

   |

**Name of Sponsor/Company:** Hill Dermaceuticals, Inc.

**Name of Finished Product:** Miconazole oil

**Name of Active Ingredient:** 2% miconazole

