At Screening/Baseline (Day 1), potentially eligible subjects will provide informed consent, and subjects will undergo screening evaluations to include a physical examination, an assessment of the signs and symptoms of otomycosis (pruritus, debris, visual examination for presence of fungal elements, and pain), and an evaluation of medical history. Urine will be obtained for pregnancy screening in female subjects of childbearing potential. Prior and concomitant medications will be reported. Subjects with positive signs and symptoms of otomycosis and who meet all other eligibility criteria will be entered into the study, and a subject global assessment of disease will be performed. Fungal and bacterial cultures of the affected ear(s) will be taken, then debris will be cleaned from the affected ear(s) following the site's normal procedures. The subject will then begin treatment with study drug. The subject or caregiver will instill the first dose of study drug at the site, under the supervision of the investigator or site personnel. Adverse events (AEs) will then be assessed. The subject will then leave the clinic and continue to administer the study drug twice per day as instructed. While in the study, subjects will be instructed to avoid getting water in the ear, to consider drying excessive water in the ear by using a blow dryer, and to place a Vaseline-impregnated cotton ball over the affected ear(s) to help keep water out of the ear while bathing or showering.

All subjects will return to the clinic on Day 8. For subjects randomized to the 7-day treatment duration, this visit will constitute the End of Treatment Visit, with procedures performed as described for that visit below. Subjects randomized to the 7-day treatment duration will not administer study drug on the day of this visit. For all other subjects, for whom this visit will constitute an On Treatment Visit, a clinical evaluation of the signs and symptoms of otomycosis, a subject global assessment, a cleaning of the affected ear(s) (following the site's normal procedures), and an assessment of AEs and concomitant medications will be performed, and these subjects will continue to administer the study drug twice per day, up through Day 14, following the same instructions as provided at the Screening/Baseline Visit on Day 1.

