### 6.2.1 Screening / Baseline

Screening procedures will occur prior to randomization and will include:

- Informed consent and assent (as applicable)
- Medical history
- Prior and concomitant medications
- Physical examination
- Urine pregnancy test (in female subjects of childbearing potential only)
- Otomycosis signs and symptoms
- Determination of subject eligibility for the study

Subjects who are eligible for the study will undergo the following additional procedures:

- Subject global assessment
- Microbial culture (fungi and bacteria)
- Ear cleaning
- Randomization
- Weighing of study drug, followed by dispensation of study drug to subject
- Dispensation of subject diary to subject.
- Administration of the first dose by the subject or caregiver under the supervision of the investigator or other study personnel
- Collection of AE information, with the time of AEs to be reported as occurring either before or after the first dose of study drug
- Subject instruction about the date on which they are to stop administering study drug (after all doses have been administered on Day 7 for the 7-day group, and after all doses have been administered on Day 14 for the 14-day groups; subjects will be instructed that study drug should be stopped on the appropriate date regardless of the date for which the next visit is scheduled)

- Subjects will be instructed to bring their bottle of study drug and the diary to the site for their next visit

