### **10.1.4 Safety Endpoints**

Safety endpoints will be the percentage of subjects with treatment-emergent AEs, with treatment-emergent defined as occurring upon or after administration of the first dose of study drug.

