### **10.5.2 Safety Analyses**

Safety summaries will be conducted using the safety population (see [Section 10.4.4](#)). All AEs occurring during the study will be recorded and classified using terminology from the Medical Dictionary for Regulatory Activities (MedDRA). All reported treatment-emergent adverse events (TEAEs), defined as any AE with an onset on or after the date of first study drug application, will be summarized by treatment group. Summaries will provide the number of subjects reporting TEAEs, system organ class, preferred term, severity, and relationship to study drug. When summarizing TEAEs by severity or relationship to study drug, each subject will be counted only once within a system organ class or a preferred term using the event with the greatest severity or causality, respectively, within each category. All reported SAEs will be summarized by the number of subjects reporting the event, system organ class, preferred term, severity, and relationship to study drug.

All information pertaining to AEs noted during the study will be listed by treatment group and subject and will include a verbatim description of the event as reported by the investigator, as well as the preferred term, system organ class, start date, stop date (if stopped), seriousness, severity, action taken regarding the study drug, corrective treatment, outcome, and relationship to the study drug. In addition, a listing of subjects who prematurely discontinue from the study due to AEs will be provided as well as a listing of subjects who report an SAE.

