n	xx	xx	xx	xx	Yes	xx (xx.x%)
Mean	xx.x	xx.x	xx.x	xx.x	No	xx (xx.x%)
SD	xx.x	xx.x	xx.x	xx.x		
Median	xx.xx	xx.xx	xx.xx	xx.xx		
Min. to Max.	xx to xx	xx to xx	xx to xx	xx to xx		
14-Day Miconazole Oil (N=xx)						
n	xx	xx	xx	xx	Yes	xx (xx.x%)
Mean	xx.x	xx.x	xx.x	xx.x	No	xx (xx.x%)
SD	xx.x	xx.x	xx.x	xx.x		
Median	xx.xx	xx.xx	xx.xx	xx.xx		
Min. to Max.	xx to xx	xx to xx	xx to xx	xx to xx		
14-Day Vehicle Oil (N=xx)						
n	xx	xx	xx	xx	Yes	xx (xx.x%)
Mean	xx.x	xx.x	xx.x	xx.x	No	xx (xx.x%)
SD	xx.x	xx.x	xx.x	xx.x		
Median	xx.xx	xx.xx	xx.xx	xx.xx		
Min. to Max.	xx to xx	xx to xx	xx to xx	xx to xx		

^a A subject was considered compliant with the dosing regimen if the subject applied at least 80% but no more than 120% of the expected applications while enrolled in the study.

SOURCE: USERNAME\SPONSOR\PROJECT\JOBNAME (DATE,TIME)

Table 14.3.2.1: Summary of Treatment-Emergent Adverse Event Characteristics
(Safety Population)
(Page 1 of 4)

	7-Day Miconazole Oil (N=xx)	14-Day Miconazole Oil (N=xx)	14-Day Vehicle Oil (N=xx)
Number (%) of Subjects Reporting At Least One Adverse Event	xx (xx.x%)	xx (xx.x%)	xx (xx.x%)
Number (%) of Subjects Reporting At Least One Serious Adverse Event	xx (xx.x%)	xx (xx.x%)	xx (xx.x%)
Number (%) of Subjects who Died	xx (xx.x%)	xx (xx.x%)	xx (xx.x%)
Number (%) of Subjects who Discontinued Study Drug due to Adverse Event	xx (xx.x%)	xx (xx.x%)	xx (xx.x%)
By Subject			
Maximum Severity			
Mild	xx (xx.x%)	xx (xx.x%)	xx (xx.x%)
Moderate	xx (xx.x%)	xx (xx.x%)	xx (xx.x%)
Severe	xx (xx.x%)	xx (xx.x%)	xx (xx.x%)
Strongest Relationship to Study Drug			
Not Suspected	xx (xx.x%)	xx (xx.x%)	xx (xx.x%)
Suspected	xx (xx.x%)	xx (xx.x%)	xx (xx.x%)

Note: Treatment-emergent adverse events are those with an onset on or after the date of first study drug application.

SOURCE: USERNAME\SPONSOR\PROJECT\JOBNAME (DATE,TIME)

Statistical Analysis Plan

Hill Dermaceuticals, Inc. HD-MCZ-PHII-DRF062016

Version: 1

Date: 30 MAY 2019

Table 14.3.2.1: Summary of Treatment-Emergent Adverse Event Characteristics
 (Safety Population)
 (Page 2 of 4)

	7-Day Miconazole Oil (N=xx)	14-Day Miconazole Oil (N=xx)	14-Day Vehicle Oil (N=xx)
By Subject			
Maximum Severity within Relationship to Study Drug			
Not Suspected			
Mild	xx (xx.x%)	xx (xx.x%)	xx (xx.x%)
Moderate	xx (xx.x%)	xx (xx.x%)	xx (xx.x%)
Severe	xx (xx.x%)	xx (xx.x%)	xx (xx.x%)
Suspected			
Mild	xx (xx.x%)	xx (xx.x%)	xx (xx.x%)
Moderate	xx (xx.x%)	xx (xx.x%)	xx (xx.x%)
Severe	xx (xx.x%)	xx (xx.x%)	xx (xx.x%)

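### The safety endpoint is defined by the first dose but tabulated by the first-dose date, so an adverse event before dosing on Day 1 counts as treatment-emergent (minor)

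*SAP*

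**What the plan says.** Each document defines treatment-emergent in two ways.

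- **By dose.** Protocol 10.1.4 sets the safety endpoint as the percentage of subjects with treatment-emergent AEs, with "treatment-emergent defined as occurring upon or after administration of the first dose of study drug". SAP 5.2 uses the same definition.
- **By date.** Protocol 10.5.2 classifies a treatment-emergent AE (TEAE) as "defined as any AE with an onset on or after the date of first study drug application", and the synopsis agrees. SAP 6.8.3 follows: "Treatment-emergent AEs (TEAEs) are defined as AEs with an onset on or after the date of the first study drug application". The notes of Tables 14.3.2.1 to 14.3.2.5 and 14.3.3.1 to 14.3.3.4 repeat it: "Treatment-emergent adverse events are those with an onset on or after the date of first study drug application".

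The Day 1 schedule in Protocol 3 determines when the two can differ: "At Screening/Baseline (Day 1), potentially eligible subjects will provide informed consent". Culture and ear cleaning follow at the same visit, and then "The subject or caregiver will instill the first dose of study drug at the site". Protocol 8.4 starts AE collection once consent is signed.

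Protocol 6.2.1 asks for the timing that would separate the two rules: "Collection of AE information, with the time of AEs to be reported as occurring either before or after the first dose of study drug". The SAP also plans Listing 16.2.7.2.2 for pre-treatment AEs. Its shell, like that of the TEAE listing 16.2.7.2.3, has a field for when the AE began. SAP 6.8.3 does not refer to the timing item or to that field.

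**The concern.** Where screening precedes dosing by days, a date rule and a dose rule seldom disagree. Here the whole scheduled pre-dose collection period falls on the first-dose date. An AE arising between consent and first instillation, for example during culture or cleaning, is a TEAE under the analysis section and not under the endpoint definition.

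The percentage of subjects with TEAEs is the only safety endpoint, so the same data can give two values for it. The exposed figures are the all-causality counts: overall, by severity, and in the *Not Suspected* rows. The date rule also undercuts two things the documents themselves provide for, namely the before/after-dose timing item and the pre-treatment listing.

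**Working it through.** The documents give no figure on this point, so the first check is a comparison of the two rules by onset time for a subject dosed as scheduled.

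| Onset of AE | Dose rule (Protocol 10.1.4, SAP 5.2) | Date rule (Protocol 10.5.2, synopsis, SAP 6.8.3, table notes) |
|---|---|---|
| Day 1, after consent, before first dose | Not a TEAE | TEAE |
| Day 1, at or after first dose | TEAE | TEAE |
| After Day 1 | TEAE | TEAE |

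Only the first row differs. Events before consent are not collected, so when consent and first dose share a date, no collected AE can precede that date. On a date rule the pre-treatment listing is then essentially empty for dosed subjects. The number of table notes that carry the date rule is 5 (14.3.2.1 to 14.3.2.5) + 4 (14.3.3.1 to 14.3.3.4) = 9.

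**Scale per affected subject.** A subject whose only AE was pre-dose moves the arm's TEAE percentage by 1/n, where n is the arm size.

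Inputs:
- About 75 subjects, randomized 1:1:1 (Protocol 3 and 9.2), in blocks of six within site (SAP 4.1.2).
- 7-Day kits are removed once that arm has at least 10 MITT subjects (SAP 6.1.6). Assumed here: removal at exactly 10.
- The MITT share is not given. Assumed range: 30% to 60%. As an anchor, Protocol 3.1 plans about 10 culture-positive completers per group, so 3 × 10 / 75 = 40%.
- Assumed: the two 14-Day arms stay equal in size.

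Steps:
1. With no change in allocation, 75/3 = 25 per arm, and 1/25 = 4.0 points.
2. The removal trigger is expected when the 7-Day arm reaches 10 divided by the MITT share. At 40% that is 10/0.40 = 25, exactly where equal allocation of 75 ends.
3. At 30%, 25 subjects in the 7-Day arm give 25 × 0.30 = 7.5 expected MITT subjects, fewer than 10. The trigger is not expected within 75 subjects, so the arms stay at about 25 and the figure stays at 4.0 points.
4. At 60%, the trigger comes at 10/0.60 ≈ 17 in the 7-Day arm. The 14-Day arms then end at (75 − 17)/2 = 29 each.

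| Assumed MITT share | 7-Day arm | Points per subject | Each 14-Day arm | Points per subject |
|---|---|---|---|---|
| 30% | about 25 | 4.0 | about 25 | 4.0 |
| 40% | 25 | 4.0 | 25 | 4.0 |
| 60% | about 17 | 1/17 = 5.9 | about 29 | 1/29 = 3.4 |

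The denominator in the tables is the safety population, which requires a dose and a post-Baseline safety assessment, so the true n may be slightly smaller.

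**The case against.** The strongest case for leaving the text alone is that the date rule is the sponsor's working choice and a common, conservative one. It appears in the synopsis, in Protocol 10.5.2, in SAP 6.8.3 and in all nine table notes, so a programmer working from the analysis sections has one rule. It over-counts rather than hides events. It also fits the only onset field that Protocol 8.4 names for each AE, which is a date. The Amendment 1 summary shows dose-based wording beside the newer date-based wording in the synopsis, and the current synopsis keeps only the latter; on that view the dose wording in Protocol 10.1.4 is left-over text. Moving SAP 6.8.3 to the dose rule would also open a new difference from Protocol 10.5.2. Finally, the SAP does not say how the pre-treatment listing is populated, and the AE listings already show when each event began.

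Part of this stands. The date rule is an acceptable resolution if it is chosen openly, and the practical effect is slight. It does not remove the contradiction. Neither document calls the date rule a convention, and SAP 5.2, dated more than two years after Amendment 1, restates the dose definition. The timing item in Protocol 6.2.1 and the planned pre-treatment listing serve little purpose under a date rule.

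Three stronger readings are tempting, and the documents do not support them:

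- **Between-arm bias.** In the Protocol 6.2.1 sequence, culture and cleaning come before randomization, so events they cause should not depend on arm.
- **Inflated drug-related counts.** Under the causality definitions in Protocol 8.3, an event before any dose should be rated not suspected, so the *Suspected* rows should not change.
- **A larger 7-Day arm at a low MITT share.** A reader might divide 10 by 0.30, get 33 subjects in that arm, and assign the rest of the 75 to the 14-Day arms. Under equal allocation, when the 7-Day arm has 33 subjects each of the others has about 33 too, a total of about 99. That cannot occur within 75.

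**Conclusion.** The inconsistency is real and is in current text: the endpoint is defined by dose and tabulated by date, and the two differ for AEs with onset before the first dose on Day 1. It is minor. The exposed interval is the pre-dose part of one clinic visit, SAP 6.8.3 plans no inference on AEs, and the number of such events is unknown and may be zero.

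If such events occur, each subject with no other AE shifts an arm's all-causality TEAE rate by about 4 points, with a range of 3.4 to 5.9 points. That range rests on 75 subjects in total, kit removal at exactly 10 MITT subjects, an assumed MITT share of 30% to 60%, and equal 14-Day arms. Later removal would pull the arms back towards 25 each. Enrolment beyond 75, which Protocol 4.4 allows, would lower the figure for arms still enrolling.

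**What to change.** First confirm that the before/after-first-dose item required by Protocol 6.2.1 is on the eCRF. The listing field for when the AE began is probably that item, but Protocol 8.4 names only the onset date.

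If the item is there, change SAP 6.8.3 and the nine table notes as follows:

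- An AE with onset on the first-dose date is classified by the before/after-first-dose item.
- If the item is missing, the AE counts as treatment-emergent.
- Later onsets are classified by date.

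Record the departure from Protocol 10.5.2 in SAP section 8, which now reports no changes, and align Protocol 10.5.2 and the synopsis at the next amendment.

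If the item is not on the eCRF, or the sponsor deliberately keeps the date rule as a conservative convention, reword Protocol 10.1.4 and SAP 5.2 to the date rule instead, and state how Listing 16.2.7.2.2 is populated.

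The first route costs SAP wording, one line of derivation code and one eCRF check. It needs no new data and no protocol amendment for this alone. Either route should be settled before unblinding.

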6.8.4. Clinical Laboratory Evaluation

Urine pregnancy test results will only be shown in a by-subject listing.

6.8.5. Physical Examination

Physical examination data will be presented in a by-subject listing.

7. DETERMINATION OF SAMPLE SIZE

The sample size for this study is not based on statistical considerations and is instead intended to be a reasonable number of subjects upon which to gather preliminary information on the efficacy and safety of miconazole oil when administered via the otic route to subjects with otomycosis.

8. CHANGES IN THE PLANNED ANALYSES

There are no changes in the conduct of the study or planned analyses.

Number of Subjects Included in the MITT Population	xx (xx.x%)	xx (xx.x%)	xx (xx.x%)
Number of Subjects Excluded from the Safety Population	xx (xx.x%)	xx (xx.x%)	xx (xx.x%)
Number of Subjects Included in the Safety Population	xx (xx.x%)	xx (xx.x%)	xx (xx.x%)
Number of Subjects Excluded from the PP Population	xx (xx.x%)	xx (xx.x%)	xx (xx.x%)
Number of Subjects Included in the PP Population	xx (xx.x%)	xx (xx.x%)	xx (xx.x%)

SOURCE: USERNAME\SPONSOR\PROJECT\JOBNAME (DATE,TIME)

Table 14.0.2: Summary of Subjects Excluded from Analyses
 (Randomized Subjects)

	7-Day Miconazole Oil (N=xx)	14-Day Miconazole Oil (N=xx)	14-Day Vehicle Oil (N=xx)
Number of Subjects Excluded from the ITT Population	xx (xx.x%)	xx (xx.x%)	xx (xx.x%)
Reason for Exclusion from the ITT Population			
Not Dispensed Study Drug	xx (xx.x%)	xx (xx.x%)	xx (xx.x%)
Number of Subjects Excluded from the MITT Population	xx (xx.x%)	xx (xx.x%)	xx (xx.x%)
Reason for Exclusion from the MITT Population			
Not Dispensed Study Drug	xx (xx.x%)	xx (xx.x%)	xx (xx.x%)
No Positive Otomycosis Diagnosis	xx (xx.x%)	xx (xx.x%)	xx (xx.x%)
Number of Subjects Excluded from the Safety Population	xx (xx.x%)	xx (xx.x%)	xx (xx.x%)
Reason for Exclusion from the Safety Population			
Not Dispensed Study Drug	xx (xx.x%)	xx (xx.x%)	xx (xx.x%)
No Post Baseline Assessment	xx (xx.x%)	xx (xx.x%)	xx (xx.x%)
Number of Subjects Excluded from the PP Population	xx (xx.x%)	xx (xx.x%)	xx (xx.x%)
Reason for Exclusion from the PP Population			
Not Dispensed Study Drug	xx (xx.x%)	xx (xx.x%)	xx (xx.x%)
No Positive Otomycosis Diagnosis	xx (xx.x%)	xx (xx.x%)	xx (xx.x%)
Violated the inclusion/exclusion criteria	xx (xx.x%)	xx (xx.x%)	xx (xx.x%)
Used an interfering concomitant medication	xx (xx.x%)	xx (xx.x%)	xx (xx.x%)
Did not attend the Test of Cure Visit	xx (xx.x%)	xx (xx.x%)	xx (xx.x%)
Have not been compliant with the dosing regimen	xx (xx.x%)	xx (xx.x%)	xx (xx.x%)
Out of visit window at the Test of Cure Visit	xx (xx.x%)	xx (xx.x%)	xx (xx.x%)

SOURCE: USERNAME\SPONSOR\PROJECT\JOBNAME (DATE,TIME)

Statistical Analysis Plan

Hill Dermaceuticals, Inc. HD-MCZ-PHII-DRF062016

Version: 1

Date: 30 MAY 2019

 Table 14.0.3: Summary of Subject Treatment Completion/Discontinuation
 (Randomized Subjects)

	7-Day Miconazole Oil (N=xx)	14-Day Miconazole Oil (N=xx)	14-Day Vehicle Oil (N=xx)
Completed Study			
Yes	xx (xx.x%)	xx (xx.x%)	xx (xx.x%)
No	xx (xx.x%)	xx (xx.x%)	xx (xx.x%)
Reason for Discontinuation			
Adverse Event	xx (xx.x%)	xx (xx.x%)	xx (xx.x%)
Lost To Follow-Up	xx (xx.x%)	xx (xx.x%)	xx (xx.x%)
Pregnancy	xx (xx.x%)	xx (xx.x%)	xx (xx.x%)
Protocol Deviation	xx (xx.x%)	xx (xx.x%)	xx (xx.x%)
Withdrawal by Subject	xx (xx.x%)	xx (xx.x%)	xx (xx.x%)
Withdrawal by Parent/Guardian	xx (xx.x%)	xx (xx.x%)	xx (xx.x%)
Physician Decision	xx (xx.x%)	xx (xx.x%)	xx (xx.x%)
Study Terminated by Sponsor	xx (xx.x%)	xx (xx.x%)	xx (xx.x%)
Other ^a	xx (xx.x%)	xx (xx.x%)	xx (xx.x%)

^a See Listing 16.2.1.2 for other discontinuation reasons.

SOURCE: USERNAME\SPONSOR\PROJECT\JOBNAME (DATE,TIME)

Table 14.1.1.1: Summary of Subject Demographics
 (Modified Intent-To-Treat Population)

	7-Day Miconazole Oil (N=xx)	14-Day Miconazole Oil (N=xx)	14-Day Vehicle Oil (N=xx)
Age (years)			
n	xx	xx	xx
Mean	xx.x	xx.x	xx.x
SD	xx.xx	xx.xx	xx.xx
Median	xx.x	xx.x	xx.x
Min. to Max.	xx to xx	xx to xx	xx to xx
Sex			
n	xx	xx	xx
Male	xx (xx.x%)	xx (xx.x%)	xx (xx.x%)
Female	xx (xx.x%)	xx (xx.x%)	xx (xx.x%)
Ethnicity			
n	xx	xx	xx
Hispanic or Latino	xx (xx.x%)	xx (xx.x%)	xx (xx.x%)
Not Hispanic or Latino	xx (xx.x%)	xx (xx.x%)	xx (xx.x%)
Race			
n	xx	xx	xx
American Indian or Alaska Native	xx (xx.x%)	xx (xx.x%)	xx (xx.x%)
Asian	xx (xx.x%)	xx (xx.x%)	xx (xx.x%)
Black or African American	xx (xx.x%)	xx (xx.x%)	xx (xx.x%)
Native Hawaiian or Other Pacific Islander	xx (xx.x%)	xx (xx.x%)	xx (xx.x%)
White	xx (xx.x%)	xx (xx.x%)	xx (xx.x%)
Other ^a	xx (xx.x%)	xx (xx.x%)	xx (xx.x%)

^a See Listing 16.2.4.1 for a complete list of all other races.

SOURCE: USERNAME\SPONSOR\PROJECT\JOBNAME (DATE,TIME)

Table 14.1.1.2: Summary of Subject Demographics
 (Per-Protocol Population)

	7-Day Miconazole Oil (N=xx)	14-Day Miconazole Oil (N=xx)	14-Day Vehicle Oil (N=xx)
Age (years)			
n	xx	xx	xx
Mean	xx.x	xx.x	xx.x
SD	xx.xx	xx.xx	xx.xx
Median	xx.x	xx.x	xx.x
Min. to Max.	xx to xx	xx to xx	xx to xx
Sex			
n	xx	xx	xx
Male	xx (xx.x%)	xx (xx.x%)	xx (xx.x%)
Female	xx (xx.x%)	xx (xx.x%)	xx (xx.x%)
Ethnicity			
n	xx	xx	xx
Hispanic or Latino	xx (xx.x%)	xx (xx.x%)	xx (xx.x%)
Not Hispanic or Latino	xx (xx.x%)	xx (xx.x%)	xx (xx.x%)
Race			
n	xx	xx	xx
American Indian or Alaska Native	xx (xx.x%)	xx (xx.x%)	xx (xx.x%)
Asian	xx (xx.x%)	xx (xx.x%)	xx (xx.x%)
Black or African American	xx (xx.x%)	xx (xx.x%)	xx (xx.x%)
Native Hawaiian or Other Pacific Islander	xx (xx.x%)	xx (xx.x%)	xx (xx.x%)
White	xx (xx.x%)	xx (xx.x%)	xx (xx.x%)
Other ^a	xx (xx.x%)	xx (xx.x%)	xx (xx.x%)

^a See Listing 16.2.4.1 for a complete list of all other races.

SOURCE: USERNAME\SPONSOR\PROJECT\JOBNAME (DATE,TIME)

Table 14.1.1.3: Summary of Subject Demographics
(Safety Population)

	7-Day Miconazole Oil (N=xx)	14-Day Miconazole Oil (N=xx)	14-Day Vehicle Oil (N=xx)
Age (years)			
n	xx	xx	xx
Mean	xx.x	xx.x	xx.x
SD	xx.xx	xx.xx	xx.xx
Median	xx.x	xx.x	xx.x
Min. to Max.	xx to xx	xx to xx	xx to xx
Sex			
n	xx	xx	xx
Male	xx (xx.x%)	xx (xx.x%)	xx (xx.x%)
Female	xx (xx.x%)	xx (xx.x%)	xx (xx.x%)
Ethnicity			
n	xx	xx	xx
Hispanic or Latino	xx (xx.x%)	xx (xx.x%)	xx (xx.x%)
Not Hispanic or Latino	xx (xx.x%)	xx (xx.x%)	xx (xx.x%)
Race			
n	xx	xx	xx
American Indian or Alaska Native	xx (xx.x%)	xx (xx.x%)	xx (xx.x%)
Asian	xx (xx.x%)	xx (xx.x%)	xx (xx.x%)
Black or African American	xx (xx.x%)	xx (xx.x%)	xx (xx.x%)
Native Hawaiian or Other Pacific Islander	xx (xx.x%)	xx (xx.x%)	xx (xx.x%)
White	xx (xx.x%)	xx (xx.x%)	xx (xx.x%)
Other ^a	xx (xx.x%)	xx (xx.x%)	xx (xx.x%)

^a See Listing 16.2.4.1 for a complete list of all other races.

SOURCE: USERNAME\SPONSOR\PROJECT\JOBNAME (DATE,TIME)

Statistical Analysis Plan

Hill Dermaceuticals, Inc. HD-MCZ-PHII-DRF062016

Version: 1

Date: 30 MAY 2019

Table 14.1.2.1: Subject Baseline Characteristics
 (Modified Intent-To-Treat Population)
 (Page 1 of 2)

	7-Day Miconazole Oil (N=xx)	14-Day Miconazole Oil (N=xx)	14-Day Vehicle Oil (N=xx)
Otomycosis Mycological Culture			
n	xx	xx	xx
Positive	xx (xx.x%)	xx (xx.x%)	xx (xx.x%)
Negative	xx (xx.x%)	xx (xx.x%)	xx (xx.x%)
Pruritus			
Subject Assessed			
n	xx	xx	xx
None	xx (xx.x%)	xx (xx.x%)	xx (xx.x%)
Mild	xx (xx.x%)	xx (xx.x%)	xx (xx.x%)
Moderate	xx (xx.x%)	xx (xx.x%)	xx (xx.x%)
Severe	xx (xx.x%)	xx (xx.x%)	xx (xx.x%)
Investigator Assessed			
n	xx	xx	xx
None	xx (xx.x%)	xx (xx.x%)	xx (xx.x%)
Mild	xx (xx.x%)	xx (xx.x%)	xx (xx.x%)
Moderate	xx (xx.x%)	xx (xx.x%)	xx (xx.x%)
Severe	xx (xx.x%)	xx (xx.x%)	xx (xx.x%)

Note: Table only includes assessments of the study ear.

SOURCE: USERNAME\SPONSOR\PROJECT\JOBNAME (DATE,TIME)

Table 14.1.2.1: Subject Baseline Characteristics
(Modified Intent-To-Treat Population)
(Page 2 of 2)

	7-Day Miconazole Oil (N=xx)	14-Day Miconazole Oil (N=xx)	14-Day Vehicle Oil (N=xx)
Debris			
n	xx	xx	xx
None	xx (xx.x%)	xx (xx.x%)	xx (xx.x%)
Scant	xx (xx.x%)	xx (xx.x%)	xx (xx.x%)
Moderate	xx (xx.x%)	xx (xx.x%)	xx (xx.x%)
Heavy	xx (xx.x%)	xx (xx.x%)	xx (xx.x%)
Presence of Fungal Elements			
n	xx	xx	xx
Absent	xx (xx.x%)	xx (xx.x%)	xx (xx.x%)
Present	xx (xx.x%)	xx (xx.x%)	xx (xx.x%)
Pain			
n	xx	xx	xx
Absent	xx (xx.x%)	xx (xx.x%)	xx (xx.x%)
Present	xx (xx.x%)	xx (xx.x%)	xx (xx.x%)
Subject Global Assessment			
n	xx	xx	xx
None	xx (xx.x%)	xx (xx.x%)	xx (xx.x%)
Minor	xx (xx.x%)	xx (xx.x%)	xx (xx.x%)
Moderate	xx (xx.x%)	xx (xx.x%)	xx (xx.x%)

Note: Table only includes assessments of the study ear.

SOURCE: USERNAME\SPONSOR\PROJECT\JOBNAME (DATE,TIME)

Table 14.1.2.2: Subject Baseline Characteristics
 (Per-Protocol Population)
 (Page 1 of 2)

	7-Day Miconazole Oil (N=xx)	14-Day Miconazole Oil (N=xx)	14-Day Vehicle Oil (N=xx)
Otomycosis Mycological Culture			
n	xx	xx	xx
Positive	xx (xx.x%)	xx (xx.x%)	xx (xx.x%)
Negative	xx (xx.x%)	xx (xx.x%)	xx (xx.x%)
Pruritus			
Subject Assessed			
n	xx	xx	xx
None	xx (xx.x%)	xx (xx.x%)	xx (xx.x%)
Mild	xx (xx.x%)	xx (xx.x%)	xx (xx.x%)
Moderate	xx (xx.x%)	xx (xx.x%)	xx (xx.x%)
Severe	xx (xx.x%)	xx (xx.x%)	xx (xx.x%)
Investigator Assessed			
n	xx	xx	xx
None	xx (xx.x%)	xx (xx.x%)	xx (xx.x%)
Mild	xx (xx.x%)	xx (xx.x%)	xx (xx.x%)
Moderate	xx (xx.x%)	xx (xx.x%)	xx (xx.x%)
Severe	xx (xx.x%)	xx (xx.x%)	xx (xx.x%)

Note: Table only includes assessments of the study ear.

SOURCE: USERNAME\SPONSOR\PROJECT\JOBNAME (DATE,TIME)

Table 14.1.2.2: Subject Baseline Characteristics
(Per-Protocol Population)
(Page 2 of 2)

	7-Day Miconazole Oil (N=xx)	14-Day Miconazole Oil (N=xx)	14-Day Vehicle Oil (N=xx)
Debris			
n	xx	xx	xx
None	xx (xx.x%)	xx (xx.x%)	xx (xx.x%)
Scant	xx (xx.x%)	xx (xx.x%)	xx (xx.x%)
Moderate	xx (xx.x%)	xx (xx.x%)	xx (xx.x%)
Heavy	xx (xx.x%)	xx (xx.x%)	xx (xx.x%)
Presence of Fungal Elements			
n	xx	xx	xx
Absent	xx (xx.x%)	xx (xx.x%)	xx (xx.x%)
Present	xx (xx.x%)	xx (xx.x%)	xx (xx.x%)
Pain			
n	xx	xx	xx
Absent	xx (xx.x%)	xx (xx.x%)	xx (xx.x%)
Present	xx (xx.x%)	xx (xx.x%)	xx (xx.x%)
Subject Global Assessment			
n	xx	xx	xx
None	xx (xx.x%)	xx (xx.x%)	xx (xx.x%)
Minor	xx (xx.x%)	xx (xx.x%)	xx (xx.x%)
Moderate	xx (xx.x%)	xx (xx.x%)	xx (xx.x%)

Note: Table only includes assessments of the study ear.

SOURCE: USERNAME\SPONSOR\PROJECT\JOBNAME (DATE,TIME)

Table 14.1.2.3: Subject Baseline Characteristics
 (Safety Population)
 (Page 1 of 2)

	7-Day Miconazole Oil (N=xx)	14-Day Miconazole Oil (N=xx)	14-Day Vehicle Oil (N=xx)
Otomycosis Mycological Culture			
n	xx	xx	xx
Positive	xx (xx.x%)	xx (xx.x%)	xx (xx.x%)
Negative	xx (xx.x%)	xx (xx.x%)	xx (xx.x%)
Pruritus			
Subject Assessed			
n	xx	xx	xx
None	xx (xx.x%)	xx (xx.x%)	xx (xx.x%)
Mild	xx (xx.x%)	xx (xx.x%)	xx (xx.x%)
Moderate	xx (xx.x%)	xx (xx.x%)	xx (xx.x%)
Severe	xx (xx.x%)	xx (xx.x%)	xx (xx.x%)
Investigator Assessed			
n	xx	xx	xx
None	xx (xx.x%)	xx (xx.x%)	xx (xx.x%)
Mild	xx (xx.x%)	xx (xx.x%)	xx (xx.x%)
Moderate	xx (xx.x%)	xx (xx.x%)	xx (xx.x%)
Severe	xx (xx.x%)	xx (xx.x%)	xx (xx.x%)

Note: Table only includes assessments of the study ear.

SOURCE: USERNAME\SPONSOR\PROJECT\JOBNAME (DATE,TIME)

Table 14.1.2.3: Subject Baseline Characteristics
(Safety Population)
(Page 2 of 2)

	7-Day Miconazole Oil (N=xx)	14-Day Miconazole Oil (N=xx)	14-Day Vehicle Oil (N=xx)
Debris			
n	xx	xx	xx
None	xx (xx.x%)	xx (xx.x%)	xx (xx.x%)
Scant	xx (xx.x%)	xx (xx.x%)	xx (xx.x%)
Moderate	xx (xx.x%)	xx (xx.x%)	xx (xx.x%)
Heavy	xx (xx.x%)	xx (xx.x%)	xx (xx.x%)
Presence of Fungal Elements			
n	xx	xx	xx
Absent	xx (xx.x%)	xx (xx.x%)	xx (xx.x%)
Present	xx (xx.x%)	xx (xx.x%)	xx (xx.x%)
Pain			
n	xx	xx	xx
Absent	xx (xx.x%)	xx (xx.x%)	xx (xx.x%)
Present	xx (xx.x%)	xx (xx.x%)	xx (xx.x%)
Subject Global Assessment			
n	xx	xx	xx
None	xx (xx.x%)	xx (xx.x%)	xx (xx.x%)
Minor	xx (xx.x%)	xx (xx.x%)	xx (xx.x%)
Moderate	xx (xx.x%)	xx (xx.x%)	xx (xx.x%)

Note: Table only includes assessments of the study ear.

SOURCE: USERNAME\SPONSOR\PROJECT\JOBNAME (DATE,TIME)

Statistical Analysis Plan

Hill Dermaceuticals, Inc. HD-MCZ-PHII-DRF062016

Version: 1

Date: 30 MAY 2019

Table 14.2.1.1: Summary of Primary Efficacy Endpoint: Therapeutic Cure at Test of Cure
 (Modified Intent-to-Treat Population)

	7-Day Miconazole Oil (N=xx)	14-Day Miconazole Oil (N=xx)	14-Day Vehicle Oil (N=xx)
Therapeutic Cure ^a at Test of Cure			
Achieved	xx (xx.x%)	xx (xx.x%)	xx (xx.x%)
Not Achieved	xx (xx.x%)	xx (xx.x%)	xx (xx.x%)

^a Therapeutic Cure is defined as a negative mycological culture plus Clinical Cure for the study ear. Clinical Cure is defined as the absence of all otomycosis signs and symptoms based on Investigator assessment according to the scales for each individual sign or symptom and with absence defined as a score of 0 on each of the scales for pruritus, debris, fungal elements, and pain.

Note: Last observation carried forward (LOCF) used to impute missing values.

SOURCE: USERNAME\SPONSOR\PROJECT\JOBNAME (DATE,TIME)

Statistical Analysis Plan

Hill Dermaceuticals, Inc. HD-MCZ-PHII-DRF062016

Version: 1

Date: 30 MAY 2019

Table 14.2.1.2: Summary of Primary Efficacy Endpoint: Therapeutic Cure at Test of Cure
(Per-Protocol Population)

	7-Day Miconazole Oil (N=xx)	14-Day Miconazole Oil (N=xx)	14-Day Vehicle Oil (N=xx)
Therapeutic Cure ^a at Test of Cure			
Achieved	xx (xx.x%)	xx (xx.x%)	xx (xx.x%)
Not Achieved	xx (xx.x%)	xx (xx.x%)	xx (xx.x%)

^a Therapeutic Cure is defined as a negative mycological culture plus Clinical Cure for the study ear. Clinical Cure is defined as the absence of all otomycosis signs and symptoms based on Investigator assessment according to the scales for each individual sign or symptom and with absence defined as a score of 0 on each of the scales for pruritus, debris, fungal elements, and pain.

Note: Last observation carried forward (LOCF) used to impute missing values.

SOURCE: USERNAME\SPONSOR\PROJECT\JOBNAME (DATE,TIME)

Statistical Analysis Plan

Hill Dermaceuticals, Inc. HD-MCZ-PHII-DRF062016

Version: 1

Date: 30 MAY 2019

Table 14.2.2.1.1: Summary of Secondary Efficacy Endpoints: Mycological Culture and Individual Signs and Symptoms
(Modified Intent-to-Treat Population)

	7-Day Miconazole Oil (N=xx)	14-Day Miconazole Oil (N=xx)	14-Day Vehicle Oil (N=xx)
Clinical Cure ^a at Test of Cure			
Achieved	xx (xx.x%)	xx (xx.x%)	xx (xx.x%)
Not Achieved	xx (xx.x%)	xx (xx.x%)	xx (xx.x%)
Negative Mycological Culture at Test of Cure			
Achieved	xx (xx.x%)	xx (xx.x%)	xx (xx.x%)
Not Achieved	xx (xx.x%)	xx (xx.x%)	xx (xx.x%)
Negative Mycological Culture and Individual Sign or Symptom Score of 0 or 1 on each of the Scales for Pruritus and Debris and a Score of 0 on each of the Scales for Fungal Elements and Pain at Test of Cure.			
Achieved	xx (xx.x%)	xx (xx.x%)	xx (xx.x%)
Not Achieved	xx (xx.x%)	xx (xx.x%)	xx (xx.x%)
Individual Sign or Symptom Score of 0 or 1 on each of the Scales for Pruritus and Debris and a Score of 0 on each of the Scales for Fungal Elements and Pain at Test of Cure.			
Achieved	xx (xx.x%)	xx (xx.x%)	xx (xx.x%)
Not Achieved	xx (xx.x%)	xx (xx.x%)	xx (xx.x%)

^a Clinical Cure is defined as the absence of all otomycosis signs and symptoms based on Investigator assessment according to the scales for each individual sign or symptom and with absence defined as a score of 0 on each of the scales for pruritus, debris, fungal elements, and pain.

Note: Last observation carried forward (LOCF) used to impute missing values.

SOURCE: USERNAME\SPONSOR\PROJECT\JOBNAME (DATE,TIME)

Statistical Analysis Plan

Hill Dermaceuticals, Inc. HD-MCZ-PHII-DRF062016

Version: 1

Date: 30 MAY 2019

Table 14.2.2.1.2: Summary of Secondary Efficacy Endpoints: Mycological Culture and Individual Signs and Symptoms Endpoints
(Per-Protocol Population)

	7-Day Miconazole Oil (N=xx)	14-Day Miconazole Oil (N=xx)	14-Day Vehicle Oil (N=xx)
